2.3.4.2. Measurements

All children will be thoroughly evaluated at baseline (before the intervention begins) and post-intervention (after the end of intervention). Evaluation includes sociodemographic profile (baseline only), dietary and lifestyle habits, anthropometric measurements, microbiome, metabolome and genotype (baseline only) profiling. Sociodemographic assessment and genotype profiling will be performed only in the observational phase and will not be repeated during the intervention Phase I.

o Sociodemographic information

Sociodemographic information will be collected from all children at baseline [21, 22], as described above.

Dietary assessment

At baseline and post-intervention the most valid method as evaluated in study phase I will be used, as described above (2.3.3 Study Phase I, Measurements: Dietary assessment). Two methods of dietary assessment will be compared during Phase I, namely a 4-day food record (supported by a mobile app for food pictures uploading) and an extensive semi quantitative food frequency questionnaire (FFQ), primarily aiming at evaluating the validity of the FFQ against the 4-day food record.

[figure not shown]
Moreover, for the evaluation of adherence to the Mediterranean Diet, the KIDMED score will be used [24], as described above.

o Other lifestyle behaviors assessment

Physical activity level, sleep duration and smoking habits will be assessed as described above. Furthermore, children will report whether they have a TV set in their room, the intake of dietary supplements and whether they are medically diagnosed with dietary allergies or other diseases as described in the former section.

Anthropometric assessment

Children's weight will be measured on leveled platform scale to the nearest 0.5 kg and height on a wall-mounted stadiometer to the nearest 0.5 cm. BMI (kg/m²) will be calculated by dividing the weight in kilograms by the height in meters squared.

Medical history assessment

Children's medical history will be recorded by asking all the chronic conditions that they may have.

Genotype characterisation

A buccal swap sample will be collected from all children at baseline. In specific, standard buccal swab kits will be used to gather DNA sample for sequencing, as described in Deliverable 3.1.

Metabolome characterisation

For the characterisation of the children's metabolic profile, urine and blood samples will be collected as described in Deliverables 2.2 and 3.1.

Microbiome assessment

Fecal samples from all children will be collected repeatedly for microbiome analyses. The protocol is described in Deliverable 2.1.

2.3.4.3. *Outcomes*

To evaluate the effectiveness of the intensive personalized dietary intervention changes in dietary, lifestyle, growth-related and metabolic factors will be assessed, as described below and in Deliverable 2.8.

Dietary factors

Changes in dietary factors are expected after the personalized intervention. In specific, energy intake, the composition of the diet in macro-nutrients, especially of saturated and trans-fatty acid intake [31] as well as specific micro-nutrients, such as vitamin D and iron [32, 33] are expected to improve. What is more, consumption of specific food groups, such as fruits and vegetables [34-37] and dairy products [37-40] is expected to change. Finally, adherence to the Mediterranean Diet is expected to increase [41].

Other lifestyle factors

Levels of children's physical activity after the implementation of the platform-derived personalised diet are expected to increase [42-44].

Growth related factors

Regarding children's weight, height and BMI status is expected to change and will be compared to the available growth charts proposed by the World Health Organization [45].

Clinical outcomes

To test the effect of the personalised diet intervention on clinical diabetes we will evaluate possible improvement in the metabolic profile of children such as blood glucose, insulin, A1C, HOMA-IR (Type II diabetes) and c-peptide (Type I diabetes) [46, 47]. In addition, cardiometabolic risk factors such as total cholesterol, LDL cholesterol, HDL cholesterol, LDL/HDL cholesterol ratio and triglycerides will be also assessed [48].

Microbiome-related factors

In the post intervention phase, changes in the gut microbiome related to dietary modifications are expected to occur [49]. We also expect to detect alteration of the metabolome profile at the systemic level (blood and urine), such as changes in the quantity of colonic short chain fatty acid [50].

2.3.5. Sample

2.3.5.1. Sample size

For **Study I phase I**, the working sample will be 200 children, 8-18 years old. By this sample size a statistical power of 92% will be achieved to evaluate two-sided correlation coefficients between the investigated measurements at the level of r = 0.33 [* power one correlation 0 .30, n(200)].

For **Study I phase II**, the required sample will be 80 children (40 per Group A or B) aged 8-18 years old, in order to achieve statistical power of at least 90% at 5% significance level of two-sided hypotheses for the evaluation of 0.75 standard deviations (SD) mean differences in the primary endpoint of the Study [power two means 100, diff (15) sd (20) n (80)].

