2.2. Objectives

The objectives of the Study I are:

- a) to assess the effectiveness of an intensive personalized dietary intervention in children with obesity and/or diabetes, versus a non-personalized one, in terms of health indices improvement, namely anthropometry, biochemical markers and dietary intake
- b) to identify possible links between biomarkers measured in urine or feces with obesity/diabetes markers

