2.3.1. Study design

The details of the study design where optimized following discussions with the NUTRISHIELD partners (during the meeting held on Athens 9-10/4/2019, mails exchange and teleconferences) to better serve the project purposes. Small deviations from the Description of Action were decided regarding the study design related to the groups and the timeline without altering the overall goals of the study.

The proposed study is a two-arm, parallel, randomized controlled study, with a dietary intervention for children (8-18 year old) with obesity or diabetes (type I or II). It will be carried out in Ospedale San Raffaele hospital between M19 to M41. The study protocol will be approved by the Ethics Committee, and written informed consent will be obtained from all caregivers and/or participants. All procedures regarding volunteers' recruitment and participation, data security and handling will be in absolute accordance with the principles set under Work Package (WP) 9, concerning Ethical Requirements, and more specifically stated on Tasks 7.1 and 7.2 and D 7.2.

H2020 Contract No 818110

The study will be divided into two phases:

- 1. **Phase I**: the **Observational** phase, lasting at least four months. During this period children will be recruited and their diet and biomarkers will be assessed once, as described below. At the end of the observational phase and recruitment period, the study will pause for nine months (from M23 to M31) in order to perform machine learning analyses, feed the platform and train the personalized nutritional algorithm with the results from the preceding assessments of the observational phase.
- 2. **Phase II**: the **Intervention** phase, lasting six months. During this period children recruited in the study will be randomly allocated to one of the two groups:
 - Group A (Intervention) will receive a NUTRISHIELD-derived personalized diet
 - **Group B (Control)** will follow the standard European dietary guidelines for obesity/diabetes, i.e. the usual care/control diet.

Diet as well as biomarkers and clinical data will be evaluated at the beginning and at the end of the intervention phase.

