2.3.6. Statistical analysis

Descriptive statistics will be used to present the characteristics of the participating children. Linear regression analyses will be performed with weight and BMI, as well as blood glucose, insulin, A1C, HOMA-IR as dependent variables and physical activity levels, children's and mother's smoking habits, nutritional status including energy intake, consumption of specific food groups and KIDMED score, medical history, genotype and metabolome as the independent variables.

Between Group comparisons for the baseline measurements of the phase II of Study I, will be performed using t-test or Mann-Whitney test, to ensure comparability of the Groups. Then, children

enrolled in the intervention diet will (Group A) be compared to those of the control diet (Group B), regarding their weight and BMI status as well as regarding the glycemic control as indicated by blood glucose, insulin, A1C, HOMA-IR (i.e., primary end points), using Repeated Measures Analysis of Variance (RMANOVA). Moreover, the 2Groups will be compared regarding various cardiometabolic risk factors such as total cholesterol, LDL cholesterol, HDL cholesterol, LDL/HDL cholesterol ratio and triglycerides, improvement in nutritional status including energy intake and consumption of specific food groups, as well as urine biomarkers, biomarkers of intestinal inflammation and microbiome profile, using the aforementioned method. All necessary adjustments (based on the baseline analyses) will be performed to ensure the robustness of the results.

The analyses will be performed by using STATA v15 software (STATA Corp LLL, College Station, TX, USA).

Finally, additional statistical analysis with the view of deriving additional insights and influences in personalised nutrition will be presented in D2.5.

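### Study I Phase I: the stated 92% power at n = 200 follows from neither the r = 0.33 in the text nor the r = 0.30 in the printed command; at two-sided 5% both give over 99%

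*Protocol*

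**What the plan says.** Protocol section 2.3.5.1 (Sample size) sets the Phase I size: "the working sample will be 200 children, 8-18 years old". It then says that with this number "a statistical power of 92% will be achieved to evaluate two-sided correlation coefficients between the investigated measurements at the level of r = 0.33". The bracketed command that closes the sentence reads "power one correlation 0 .30, n(200", that is, a one-sample test of a null correlation of 0 against an alternative of 0.30 with 200 children.

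No significance level is attached to Phase I. The next paragraph, on Phase II, works "at 5% significance level of two-sided hypotheses". No allowance for dropout is stated for Phase I. Section 2.3.1 says of that phase: "During this period children will be recruited and their diet and biomarkers will be assessed once".

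The calculation serves objective (b) in section 2.2, which is "to identify possible links between biomarkers measured in urine or feces with obesity/diabetes markers".

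**The concern.** One sentence carries two target correlations, 0.33 in the text and 0.30 in the command. Both values are legible and the command is complete with its sample size, so this does not look like damage from text extraction. The power attached to them is also too low for 200 children at either value. Sample size, correlation and power cannot all be as printed unless a significance level stricter than any in the document was used.

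This sentence is the only justification given for enrolling 200 children, each of whom provides blood, urine, faecal and buccal samples. A reader, an ethics committee or a funder cannot tell whether the correlation, the power or the significance level is misreported, and so cannot say what size of association the study was designed to detect.

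**Working it through.** **Inputs**
- n = 200, null correlation 0, two-sided (section 2.3.5.1, text and command).
- r = 0.33 (text) or r = 0.30 (command).
- Significance level 0.05. This is an assumption: it is the level given for Phase II, and the printed command sets no other.

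**Formula.** With Fisher's z, power = Φ(atanh(r)·√(n − 3) − z), where z = 1.960 for two-sided 5%. The opposite tail is negligible. √197 = 14.036.

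**The plan's figure at its own inputs**
- r = 0.33: atanh = 0.3428; 0.3428 × 14.036 = 4.812; 4.812 − 1.960 = 2.852; power = 99.8%.
- r = 0.30: atanh = 0.3095; 0.3095 × 14.036 = 4.344; 4.344 − 1.960 = 2.384; power = 99.1%.

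Adding the small-sample bias term r/(2(n − 1)) gives 99.8% and 99.2%. A noncentral t calculation gives 99.8% and 99.3%. Simulation with 40,000 runs per value gives 99.8% and 99.1%. The stated 92% is not reproduced.

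**What 92% would correspond to.** The normal quantile for 92% is 1.405, so atanh(r)·√(n − 3) must equal 1.960 + 1.405 = 3.365.
- At n = 200: atanh(r) = 3.365 / 14.036 = 0.2397, so r is about 0.235.
- At r = 0.33: n = (3.365 / 0.3428)² + 3 = 99.3, so 100 children (99 with the bias term).
- At r = 0.30: n = (3.365 / 0.3095)² + 3 = 121.2, so 122 children (121 with the bias term).

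**Other settings at n = 200**

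| Setting | r = 0.30 | r = 0.33 |
|---|---|---|
| One-sided 5% | 99.7% | 99.9% |
| Two-sided 1% | 96.2% | 98.8% |
| Two correlations compared, 100 per group, two-sided 5% | 58% | 67% |
| Two-sided level that would give 92% | about 0.003 | about 0.0006 |

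A null of 0.10 instead of 0 would give 92.7% at r = 0.33, but the command prints a null of 0.

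**Scope.** The Phase II statement in the same section does agree with its own command: 15/20 = 0.75; 0.75 × √(40/2) = 3.354; 3.354 − 1.960 = 1.394; power 91.8%, which meets the stated minimum of 90%. The error is confined to Phase I.

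**The case against.** The best defence is that the error is on the safe side. Power is understated, 200 children are more than a single correlation of 0.30 or 0.33 requires, Phase I is exploratory, and the randomised comparison has its own calculation. All of that stands, and it limits the point to a correction of the sample-size statement.

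A second defence is that 5% is assumed for Phase I, and a stricter level could give 92%. That is true, but the level would have to be about 0.003 or 0.0006, and none is stated. If one was intended, leaving it out is itself what needs correcting. Likewise, 92% might have been computed for a smaller sample, since 100 children at r = 0.33 give 92.4% and 120 at r = 0.30 give 92.0%. The document mentions no such number, and no Phase I attrition that would lead to it.

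A reader might go further. Section 2.3.6 relates six outcomes to many predictors, including "medical history, genotype and metabolome as the independent variables", and one could infer that uncorrected testing at 5% will put false biomarker links into the algorithm's training data. The documents do not support this. Multiplicity handling may sit in an analysis plan that is not shown. The number of tests is not given. No section says that associations are selected by significance and passed to the algorithm; sections 2.3.1 and 2.3.4.1 describe machine-learning analyses instead. For the same reasons the surplus power cannot be credited with covering any particular number of tests.

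**Conclusion.** The point holds as an error of arithmetic and internal consistency. The text and the command give different target correlations, and 92% is wrong for both at two-sided 5%: the power of a single test is 99.8% at r = 0.33 and 99.1 to 99.2% at r = 0.30. The discrepancy is about 7 to 8 percentage points of power. Put as effect size, 200 children have 92% power for r of about 0.235, not 0.33.

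The power figures rest on the assumed two-sided 5% level; the mismatch between 0.33 and 0.30 rests on no assumption.

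It would be a mistake to read this as showing that Phase I is underpowered, because the error runs the other way. Nor does it show that enrolment should be cut to 100 or 122: those numbers only show what the stated target would imply, and the Phase I data are also meant for training the algorithm (section 2.3.1), for which the protocol gives no separate size calculation.

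**What to change.** In section 2.3.5.1, state one target correlation and the Phase I significance level, make the command match the text, and restate the power that follows from them. At two-sided 5%, either of these would be correct for n = 200:
- power of over 99% for a single correlation of 0.30 or 0.33, with whichever value the sponsor intends named in both places; or
- power of 92% for a single correlation of about 0.235.

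Add that the figure applies to a single correlation test. If a stricter level was used to reach 92%, print it in the text and in the command.

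The cost is one corrected sentence and one corrected command. Enrolment, assessments and the planned analyses are unchanged.

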2.3.5.2. Randomisation

The randomisation, either to Group A or Group B, will be performed by an 2X2 block randomization on the basis of age of children (i.e., ≤12 and >12 years old, 1:1 ratio) and sex of children (1:1 ratio). The random allocation sequence (i.e., sequentially numbered containers), will be developed using STATA v15.0 software and relevant commands. Specifically, stream random-number generators will be used. One seed value will set and then using the software and particularly a stream version of the 64-bit Mersenne Twister, Stata's default pseudorandom-number generator, a random sequence of binary numbers will be created that allocate children to each study's Group.

2.3.5.3. Blinding

The physicians and all contributors to the project who will be responsible for baseline analysis and interpretation (apart from the clinical dietitians who will be involved in dietary counselling) along with the biostatisticians will be blind to the intervention groups. Considering that the blinding of clinical dietitians is not amendable, those will be randomly assigned to either the intervention or the control group in order to reduce the risk of bias.

2.3.6. Statistical analysis

Descriptive statistics will be used to present the characteristics of the participating children. Linear regression analyses will be performed with weight and BMI, as well as blood glucose, insulin, A1C, HOMA-IR as dependent variables and physical activity levels, children's and mother's smoking habits, nutritional status including energy intake, consumption of specific food groups and KIDMED score, medical history, genotype and metabolome as the independent variables.

Between Group comparisons for the baseline measurements of the phase II of Study I, will be performed using t-test or Mann-Whitney test, to ensure comparability of the Groups. Then, children

enrolled in the intervention diet will (Group A) be compared to those of the control diet (Group B), regarding their weight and BMI status as well as regarding the glycemic control as indicated by blood glucose, insulin, A1C, HOMA-IR (i.e., primary end points), using Repeated Measures Analysis of Variance (RMANOVA). Moreover, the 2Groups will be compared regarding various cardiometabolic risk factors such as total cholesterol, LDL cholesterol, HDL cholesterol, LDL/HDL cholesterol ratio and triglycerides, improvement in nutritional status including energy intake and consumption of specific food groups, as well as urine biomarkers, biomarkers of intestinal inflammation and microbiome profile, using the aforementioned method. All necessary adjustments (based on the baseline analyses) will be performed to ensure the robustness of the results.

The analyses will be performed by using STATA v15 software (STATA Corp LLL, College Station, TX, USA).

Finally, additional statistical analysis with the view of deriving additional insights and influences in personalised nutrition will be presented in D2.5.

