2.3.3.1. Measurements

Measurements concern sociodemographic information, dietary and other lifestyle behaviors, anthropometry, medical history, genotype, metabolomics profile (in blood and urine), and microbiome.

o Sociodemographic information

Sociodemographic information will be collected from all children [21, 22]. In specific, the age (in years), the number of people living with (in the family and in the household), whether they attend school (yes/no), and whether the school is private (yes/no) will be recorded. Furthermore, information will be collected regarding parents' marital status (1; married, 2; unmarried/co-habiting, 3; single parent, 4; divorced or separated, 5; widowed), parent's origin (1; White, non-Hispanic; 2; Black, non-Hispanic; 3, Hispanic; 4, Asian; 5, other), years of education described by the number of educational years (mother and father separately), the maternal and the paternal occupation [1, unemployed; 2, employee in private sector; employee in public sector; 3, self-employed; 4, working without pay in family business; 5, on leave (excluding maternity); 6, pensioner]. Finally, the mother or the father will be asked to self-characterise their annual family and household income (ranging from 1, 0-4,999 € to 9, over 50,000 €) and whether the child has active health insurance (yes/no).

Dietary assessment

Three methods of dietary assessment will be employed during Phase I, namely a 4-day food record supported by a mobile app (for food pictures uploading), an extensive semi-quantitative food frequency questionnaire (FFQ) and a short questionnaire assessing diet quality (KIDMED). We aim to cross-match intake data, and compare the validity of the FFQ against the 4-day food record. The dietary assessment modality that proves to be the most valid will be used in phase II and, finally, in the platform. The mobile app will be developed in the context of WP6, and will serve as an adjunct to the 4-day food record, so as to examine its additive value in improving dietary assessment of children. Finally, the KIDMED will be used as a quick index of dietary quality, which can be easily incorporated in the platform. All the dietary assessment means will be thoroughly described below.

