Finally, intake of dietary supplements (e.g. vitamins) will be recorded and all children will be also asked whether they are medically diagnosed with dietary allergies or other diseases [1, lactose intolerance; 2, celiac disease; 3, medical diseases under restrictive dietary schemes (sub-question-please refer); 4, other (please refer)] and whether they follow a vegetarian (all sub-types) or vegan diet (yes/no). If the answer to the former question is positive they will be asked for further details [1, vegan; 2, lacto-vegetarian; 3, ovo-vegetarian; 4, lacto-ovo vegetarian; 5, other (please refer)].

Anthropometric assessment

Children's weight will be measured on leveled platform scale to the nearest 0.5 kg and height on a wall-mounted stadiometer to the nearest 0.5 cm. Body Mass Index (BMI) (kg/m²) will be calculated by dividing the weight in kilograms by the height in meters squared.

Medical history assessment

Children's medical history will be recorded by asking all the chronic conditions that they may have.

Genotype characterisation

A buccal swap sample will be collected from all children. In specific, standard buccal swab kits will be used to gather DNA sample for sample, as described in Deliverable 3.1.

Metabolome characterisation

For the characterisation of the children's metabolic profile, urine and blood samples will be collected as described in Deliverables 2.2 and 3.1.

Microbiome assessment

Fecal samples from all children will be collected for microbiome analyses. The protocol is described in Deliverable 2.1.

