2.3.4. Study Phase II

2.3.4.1. Description of the Intervention

Personalized diet (Group A)

This intervention includes a personalized dietary plan derived from NUTRISHIELD platform. This plan will be based on the personalized nutrition algorithm taking into account genome analysis, dietary assessment, biochemical markers, socioeconomic status as well as any input having possibly emerged from the machine learning analyses from the evaluations performed during Study Phase I. In specific, in the beginning of the intervention period, taking into account the results from the evaluations performed in the observational period, a 4-week personalized dietary plan, derived as described above will be given to the children. Then, every month, for the following six months, visits will be arranged in the hospital with a window of ± one week, in order to perform the evaluations described below and the children to receive the new 4-week algorithm-derived dietary plans based on the previous month's evaluation. The intervention will be based on dietary guidelines presented in Table 1 [30], modified accordingly to address personal dietary, genetic and other needs, if important input emerges from Phase I.

Usual care diet (Group B)

The control dietary plan will be based on the same principles as the intervention diet [30], but without the use of the NUTRISHIELD platform and the personalized algorithm. Standard information and advice will be given instead by trained dieticians in face to face meetings. This phase will last six months and visits will be arranged once per month.

Table 2.1: Evidence-based guidelines on which intervention and usual care dietary plans will be based upon[30]

Guidelin	es
0	caloric restriction of 10% below energy needs
0	fat intake of 25-35% of total energy intake
0	saturated fatty acids <10% total energy intake
0	monounsaturated fatty acids >10% total energy intake
0	adequate mixture of n-6 and n-3 polyunsaturated fatty acids (PUFA, approximately 10 $\%$ of total energy
	intake)
0	fruit intake:
	o 1.5 cups per day for children 8-13 years old
	o 1.5 cups per day for girls aged 14-18 years
	o 2 cups for boys aged 14-18 years old
0	vegetables intake:
	o 1 cup per day for girls aged 8 years old
	o 1.5 cups per day for boys aged 8 years old
	o 2 cups per day for girls aged 9-13 years old
	o 2.5 cups for boys aged 9-13 years old
	o 2.5 cups per day for girls aged 14-18 years old
	o 3 cups per day for boys aged 14-18 years old

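### The section 2.3.6 regressions use raw weight and BMI at ages 8-18 without age or sex as predictors, and leave out the fecal markers named in objective (b)

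*Protocol*

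**What the plan says.** Objective (b) of Study I (Protocol 2.2) is "to identify possible links between biomarkers measured in urine or feces with obesity/diabetes markers".

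The analysis that comes closest to it is the first paragraph of 2.3.6: "Linear regression analyses will be performed with weight and BMI, as well as blood glucose, insulin, A1C, HOMA-IR as dependent variables". The predictors are "physical activity levels, children's and mother's smoking habits, nutritional status including energy intake", followed by "consumption of specific food groups and KIDMED score, medical history, genotype and metabolome as the independent variables". The list carries no open-ended wording and no covariate clause.

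Four other places bear on how to read it:

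- **Population.** Sections 2.3.2 and 2.3.5.1 set the age range at 8-18 years and the Phase I sample at 200 children.
- **Outcome scale.** Section 2.3.3.1 computes BMI as weight over height squared, with no age or sex standardisation. The only reference to growth charts is in the Phase II outcomes (2.3.4.3), where weight, height and BMI status "will be compared to the available growth charts proposed by the World Health Organization".
- **Meaning of metabolome.** Section 2.3.3.1 lists the Phase I measurements as ending in "genotype, metabolomics profile (in blood and urine), and microbiome", and says "For the characterisation of the children's metabolic profile, urine and blood samples will be collected". The metabolome is thus blood and urine. The fecal microbiome is a separate measurement, and every child gives a sample for it.
- **Age and sex.** Age is recorded in Phase I (2.3.3.1), and age and sex are the two randomisation factors in Phase II (2.3.5.2).

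**The concern.** In growing children weight and BMI rise with age, so the same kg/m² does not represent the same adiposity at 8 as at 18. If a predictor also moves with age or sex, an unadjusted regression picks up growth as if it were a link with obesity. The protocol's own Table 2.1 suggests that diet does so. Its vegetable target rises from 1 to 2.5 cups in girls between age 8 and ages 14-18. In boys it rises from 1.5 cups to "3 cups per day for boys aged 14-18 years old". Whole-grain targets rise from 4 to 6 oz in girls and from 5 to 7 oz in boys. These are targets and not observed intakes, but they show the direction.

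Section 2.4 expects Phase I to bring out new associations between biomarkers and childhood obesity or diabetes. Associations produced by growth would weaken that output.

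The second part is coverage. Objective (b) names urine and feces. Urine enters the regressions through the metabolome, but nothing fecal does. Microbiome profile and markers of intestinal inflammation appear in 2.3.6 only as Phase II outcomes compared between diets. That comparison does not test their link with obesity or diabetes markers.

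**Working it through.** **1. Which measurements reach the regressions.** Section 2.3.3.1 names sociodemographic information, diet and lifestyle, anthropometry, medical history, genotype, metabolome and microbiome. Section 2.3.6 uses anthropometry as an outcome, and diet and lifestyle, medical history, genotype and metabolome as predictors. The two domains left out are sociodemographic information, which holds age, and microbiome.

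**2. Whether another sentence restores them.** The promise of necessary adjustments in 2.3.6 closes the paragraph on the Phase II group comparison. The WHO charts are in the Phase II outcomes. By contrast, the parallel paragraph for Study II (3.3.6) does name covariates: prematurity, age and years of education.

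**3. The plan's nearest figure.** The protocol gives no figure for confounding. Section 2.3.5.1 states 92% power for a correlation of 0.33 (0.30 in the command) with n = 200. With the Fisher z formula, power = Φ(atanh(r)·√197 − 1.96), two-sided 5%:

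- r = 0.30: Φ(0.3095 × 14.036 − 1.96) = 99.1%
- r = 0.33: 99.8%

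The stated 92% is not reproduced. That is a separate matter, and nothing below depends on it.

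**4. Illustration with one marker.** Assume a marker has no link with BMI given age. Its unadjusted correlation with BMI is then r(age, BMI) × r(age, marker). Both correlations are assumptions; the documents give neither. The rejection rate uses the Fisher z formula above with both tails. The last two columns come from 4,000 simulated data sets per row, with ages uniform on 8-18 and n = 200.

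| r(age, BMI) | r(age, marker) | Spurious r | Flagged, formula | Flagged, simulated without age | Flagged, simulated with age |
|---|---|---|---|---|---|
| 0.3 | 0.3 | 0.09 | 24.5% | 24.6% | 5.0% |
| 0.5 | 0.3 | 0.15 | 56.4% | 56.6% | 4.5% |
| 0.5 | 0.5 | 0.25 | 94.8% | 95.2% | 5.6% |
| 0.6 | 0.5 | 0.30 | 99.1% | 99.3% | 4.4% |

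**5. Illustration with joint entry.** Suppose k other predictors, each correlated c with age and otherwise independent, are in the same model. They leave a fraction v = 1/(1 + k·c²/(1 − c²)) of the age variance unexplained. Write a = r(age, BMI) and m = r(age, marker). The partial correlation is a·m·v / √[(1 − a² + a²v)(1 − m² + m²v)], tested with √(200 − 3 − k). Take a = 0.6 and m = 0.4:

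- k = 0: r = 0.24, flagged 93%.
- k = 5, c = 0.4: v = 1/(1 + 5 × 0.190) = 0.51; r = 0.123/0.872 = 0.14, flagged 50%.
- k = 10, c = 0.5: v = 1/(1 + 10 × 0.333) = 0.23; r = 0.055/0.796 = 0.07, flagged 16%.

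Joint entry reduces the problem but does not remove it. Section 2.3.6 does not say how the predictors enter.

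**The case against.** The strongest reply is that these are exploratory regressions in a document that calls its design preliminary, and that confounder sets are often left to an analysis plan. The paragraph is not labelled Phase I, and it does not say that no covariates will be added. That would answer a silent protocol. This one writes out its predictors, and the list it writes lacks the two most obvious ones. The Phase I reading follows from the order of the text and from objective (b).

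A second reply concerns size. Every correlation above is assumed, and the two-variable rates are not those of a model with many predictors. This stands: the percentages show that the effect can be large, not how large it will be here.

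Four stronger readings are tempting, and the documents do not support them.

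- **The fecal question goes unanalysed.** Section 2.3.5.1 sizes Phase I for correlations among the measurements, section 2.3.1 plans machine learning on the Phase I assessments, and 2.3.6 defers further analyses to D2.5. Any of these could include fecal data, though none says so.
- **Confounded regression results train the personalised algorithm.** Section 2.3.1 describes training by machine learning on the assessments. No section feeds the 2.3.6 regression results into it.
- **The glycemic outcomes are confounded in the same way.** The growth argument is made for weight and BMI. The documents offer nothing comparable for glucose, insulin, A1C or HOMA-IR.
- **Diagnosis is missing as well.** Medical history is a listed predictor and may already capture it.

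**Conclusion.** The point holds in two parts.

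First, run as written, the weight and BMI regressions can report growth-related markers and dietary measures as associated with obesity. This rests on the text of 2.3.6, the 8-18 age range and the unstandardised BMI. It also assumes that some predictors change with age or sex. The illustrative two-variable range is about 25% to 99% of analyses flagged for a spurious r of 0.09 to 0.30, against about 5% with age in the model. The rate is lower under joint entry with other age-related predictors.

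Second, the listed regressions do not address the fecal part of objective (b). This is a gap in the stated models, not proof that fecal data will go unanalysed.

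The consequence is limited to the observational associations. The randomised comparison of Groups A and B does not depend on these regressions.

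**What to change.** In the first paragraph of 2.3.6:

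1. Replace raw weight and BMI as dependent variables with the WHO BMI-for-age z-score, since the WHO charts are already named in 2.3.4.3. Alternatively, keep the raw outcomes and add age and sex as covariates. One of the two is enough for BMI, because the z-score is already referenced to age and sex.
2. Include age and sex in the regressions for glucose, insulin, A1C and HOMA-IR as routine adjustment.
3. Add the fecal/microbiome markers to the independent variables.
4. Optionally, state whether medical history includes the diagnosis (obesity, type I or type II diabetes); if not, a diagnosis term can be added.

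No new data are needed. Age, weight, height and fecal samples are collected in Phase I. Sex is a randomisation factor in 2.3.5.2 and is asked in the activity questionnaire (5.5). The cost is analysis wording and a few degrees of freedom out of 200.
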